(1) Due to restrictions associated with the COVID-19 pandemic, this study will be delivered in a remote format. Enrolled families will complete surveys via an electronic device connected to the internet, and intervention sessions will similarly be offered in a virtual (phone or video conferencing) format. When restrictions associated with the COVID-10 pandemic are eased, the survey, behavioral, RSA, and intervention components of this study will be conducted in research laboratories at the Frances Payne Bolton School of Nursing and the Department of Psychology at Case Western Reserve University. The intervention session component of this study will be conducted at private community locations (e.g., library meeting rooms) that are convenient for enrolled study participants once covid-19 restrictions are eased. (2) Using an existing collaboration with the Cleveland Metro School District, participants will be recruited from parent meetings, the community at large, public bus system, and Facebook advertisements. (3) Due to the COVID-19 pandemic, assent/consent will be obtained online using a REDCap survey facilitated by a phone call with a research assistant to verify understanding of the study. When restrictions associated with the COVID-19 pandemic are eased, assent/consent will be obtained in-person using the following process. First, consent/assent will be obtained at either PI [name]’s research space at the School of Nursing or [name] research space at the Department of Psychology. Next, participants will complete surveys on tablet computers either PI [name]’s research space at the School of Nursing or [name] research space at the Department of Psychology. Parent/teen dyads will then be taken to Co-I [name]’s lab at the Department of Psychology where they will be seated in comfortable chairs in separate, quiet research rooms. Research assistants will then provide an overview of the physiological equipment, including the manner of attaching all recording sensors.

Consent Process

Indicate whether you will be obtaining consent:

Yes No

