- h. **Intervention group protocol:** Due to restrictions associated with the COVID-19 pandemic, we will deliver both types of interventions in remote format wherein parents and adolescents will review video recordings of the materials, engage in exercises, and complete pre- and post-test to ensure engagement. Following the easing of restrictions associated with the COVID-19 pandemic, we will resume offering in-person sessions with parent-adolescents in groups of approximately five dyads. Each of eight 90-minute weekly sessions of the TRUST intervention will include both a trust-building topic and a depression management topic. Trust-building topics include honesty, reliability, and emotional connection.⁸ The honesty portion will include discussion and practice of disclosing personal truths and receptivity of others' disclosures. The reliability portion will include discussion and practice of making and keeping promises. The emotional connection portion will include discussion of adolescent-parent similarities and bonding activities like hugging and eye contact. The depression management portion will focus on sleep, stress management, medication adherence, and appointment keeping skills. The intervention will build depression management knowledge, set personal and dyad goals, and practice self-monitoring. Goal-setting and self-monitoring of progress are also forms of making and keeping promises, thus connecting and reinforcing the concepts of trust and depression management techniques. The **Depression Management group** will receive 8 sixty-minute weekly sessions that include the only the depression management training (sleep, stress management, medication adherence, appointment keeping) described above. Both intervention groups will be led by interventionists with health behavior change training.

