The interventionist will have a teaching plan with guidelines on time use for TRUST topics. Each session will include a trust-building topic and a depression management topic, a discussion portion and a practice portion. With the trust building portion, we will focus on honesty, reliability, and emotional connection. For example, the Honesty portion will teach adolescent and parent to share personal details about themselves without judging one another. Parents often get upset when their adolescent shares personal details with them and then jump to conclusions, judgment, and reprimands, which breaks down trust. The intervention will discuss this, then have adolescent-parent dyads practice sharing small truths and being receptive to those disclosures. With the Reliability portion, we'll discuss that reliability means following through on your word. Dyads will make small promises to one another, then try to follow through on keeping the promises in the week between sessions. Emotional Connection is built when each person is receptive to disclosures and keeps promises.

With the depression self-management portion, we will focus on stress management, sleep, medication adherence, and appointment keeping only. We will discuss why these topics are important to health and identify ways to improve them. Each adolescent-parent dyad will set goals to improve in each of these areas, then

identify a way to do that. For example, with stress management it could be taking a walk to de-stress, with sleep it might be giving up screen time one hour before bed. Making goals and keeping them is also a form of making promises and keeping them--thus connecting and reinforcing the concepts of trust and a healthy lifestyle.

We will conduct fidelity monitoring of the intervention groups. Each session of the TRUST intervention will be audio-recorded. Half of the sessions will be randomly selected for review using an investigator-developed fidelity checklist composed of the key elements of the intervention ²⁶. Fidelity will be assessed by checking that each of the assigned topics from the teaching plan are discussed during the appropriate meetings.

This is a social/behavioral research study. No drugs or devices will be tested as interventions with the research participants. No source records, such as medical or educational records, will be used to collect data about participants.

(4) Study Procedures and Time Requirement:

Study Procedures	Estimated time requirement	

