Participants participating in this research may learn new skills for better managing their stress and sleep quality; medication adherence and appointment keeping skills may improve their health; and trust-building exercises may improve the quality of the adolescent-parent relationship. These improvements may be short-term or long-term changes. We anticipate that our findings will demonstrate the linkages between a trust-building behavior change strategy and health behavior change that will help adolescents and parents improve their health.

Withdrawal of Research Participants

Research participants will be withdrawn from the intervention without their consent under these circumstances:

1. participants display disruptive behavior during the group intervention sessions,
2. evidence of abuse between parent and adolescent dyad, or
3. indication that a participant may be a harm to themselves or others.

In the event that participants are removed from the intervention, PI [name] will notify participants of their removal. Participant dyads will receive a closeout packet, which will contain a list of community resources for further depression symptom management treatment. Participants will also receive study personnel contact information to follow up on study outcomes. At this time, we will also update participants' contact information and ask if they are willing to be contacted for further study visits, if appropriate.

Alternatives to Participation

HRP-503BIO	Biomedical Protocol	
Approved:	1/23/2018	Prior Version:

- (1) No one will be required to participate in our study. Other available clinical treats are individual, family, or group therapy. Community self-management treatments available include stress management classes, such as yoga.
- (2) Standard of care therapy, including depression medication and counseling, should be continued regardless of participation. Self-management treatments are considered adjuvant to clinical treatment. We anticipate and encourage our participants to continue standard of care therapy.
- (3) Since self-management training is adjuvant to standard of care treatment, another option is to not participate.

Costs to Research Participants

- (1) There are no costs to participation in this study. Our study compensates participants for their time and travel costs.
- (2) Participants' health insurance will not be charged for any services provided in this study.

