by the sponsor and the CWRU IRB. As they occur, all unanticipated events and adverse events will immediately be reported to the PI who will report them to the IRB according to the IRB protocol reporting procedures for both serious and non-serious adverse event and unanticipated problem reporting. These will be summarized in the twice annual reports to the DSMC. Annual progress reports to the IRB and the sponsor will include a summary of the DSMC's activities and findings as well as any adverse events regarding human participants. Program Officials of the sponsor will be informed in a timely manner (3 business days) of unanticipated problems (e.g., a data breach) or unexpected serious adverse events that may be related to the study protocol or IRB-approved revisions to the study protocol that indicate a change in risk for participants.

(2) A Data and Safety Monitoring Committee (DSMC) will be established for this study. This DSMC will independent of the study sponsor and will meet every 6 months of the study. [name] will chair the committee and be responsible to submit reports to the study sponsor and IRB within 2 weeks of the meeting. DSMC members include:

[name], an experienced family researcher ([contact])
 [name], an NIH-funded researcher with parent/child dyads ([contact])
 [name], a statistician not involved with the project ([contact])
 [name], neuroscience of health behavior researcher ([contact])
 [name], PI ([contact])
 [name], Co-I ([contact])

Community-Based Participatory Research: N/A

Non-Local Recruitment Methods for Multi-Site Studies: N/A

Multi-Site Research Communication Plan: N/A

Drugs or Devices: N/A

3. Avenevoli S, Swendsen J, He J, Burstein M, Merikangas K. Major depression in the National Comorbidity Survey-Adolescent Supplement: Prevalence, Correlates, and Treatment. *Journal of the American Academy of Child & Adolescent Psychiatry*. 54(1):37-44.e32.
4. [name] HK, Lee D, Moore SM. Trust of healthcare provider varies by level of depressive symptoms in adolescents. Society of Adolescent Health & Medicine; March 14, 2018, 2018; Seattle, WA.

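### The protocol describes remote sessions both as live contact and as recordings; under recordings alone, adverse events between surveys would rest on spontaneous report

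*Combined protocol and SAP*

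**What the plan says.** **Remote format.** Setting (1) states that "intervention sessions will similarly be offered in a virtual (phone or video conferencing) format". Study Design, Procedures, and Timeline, item h, says that in the remote format of both arms "parents and adolescents will review video recordings of the materials, engage in exercises, and complete pre- and post-test to ensure engagement". Item h also says "Both intervention groups will be led by interventionists with health behavior change training", and its fidelity paragraph says "Each session of the TRUST intervention will be audio-recorded". Neither of these last two statements is limited to in-person delivery. In-person groups of about five dyads are to resume once restrictions ease.

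**Provisions written around staff contact.** Withdrawal of Research Participants gives three grounds for removal from the intervention. The first is that "participants display disruptive behavior during the group intervention sessions", the second is "evidence of abuse between parent and adolescent dyad", and the third is a sign that a participant may harm themselves or others. Vulnerable Populations (2), item c of the procedures and Risks to Research Participants (1) promise that a research assistant and the parent will be on hand if the adolescent becomes upset. The Consent Process section has staff ask participants how the study is going at each study visit.

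**Adverse events.** Provisions to Monitor the Data (1) says "As they occur, all unanticipated events and adverse events will immediately be reported to the PI". Summaries then go to the DSMC twice a year. No schedule or method for asking about events is given.

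**The TRUST exercise.** The honesty component has dyads practise sharing personal details. Item h observes that parents are often upset by such disclosures and then "jump to conclusions, judgment, and reprimands, which breaks down trust". The risk section lists loss of confidentiality, discomfort with questions, stigma and disappointment with the assigned group. It does not list conflict after a disclosure.

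**The concern.** The safety provisions read as if a member of staff is present or in contact while dyads work through the sessions. One of the two descriptions of remote delivery has no such contact. If that is the format in use, a quarrel or upset set off by an exercise at home reaches the study only if somebody reports it unprompted.

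This matters most for TRUST, because it alone contains the disclosure exercise, so a comparison of session-related upset between arms is of real interest. A low count obtained by passive reporting would be hard to interpret: it could mean few events or few reports. The parent, who is the other named source of comfort, may also be the other party to the conflict. Item b allows a household with one device to pass it from adolescent to parent, which does not make unprompted reporting easier.

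**Working it through.** No figure in the plan can be reproduced here. The check sets the provisions against the two readings of the remote format.

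| Provision and place | If sessions are live by phone or video | If dyads use recordings alone |
|---|---|---|
| Removal for group disruption (Withdrawal) | An interventionist can see or hear it | No group and no observer |
| Removal for abuse or risk of harm (Withdrawal) | May surface in session or elsewhere | May still surface through questionnaires, calls or reports; no source is specified |
| Research assistant's support (Vulnerable Populations (2); item c; Risks (1)) | Possible, though not described | No remote form described |
| Parent, crisis numbers, mobile crisis team | Available | Available |
| Psychologist's review of worrying questionnaires | Works | Works, for severe depression or suicidal ideation |
| Check-in at study visits (Consent Process) | Not tied to sessions | Not tied to sessions; surveys go out as an emailed link (item b) and no remote version of the check-in is described |
| Adverse event reporting (Provisions to Monitor (1)) | Session staff can notice and report | Rests on spontaneous report |

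**Timing.** Sessions run weekly for 8 weeks. Surveys are at baseline, 3 and 6 months, and 3 months is about 13 weeks (52/4). All 8 sessions can therefore fall between two consecutive surveys. The remote pre- and post-tests are the only other described data points in that interval. Their stated purpose is engagement, no safety content or staff review is described, and it is not said whether there is one pair per session or one per programme.

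**The time table does not settle the format.** Study Procedures and Time Requirement (4) gives weekly sessions of 45 minutes and 1 hour for the two groups. Item h gives 60 minutes for Depression Management and 90 for TRUST. Nothing says whether the shorter times belong to the remote format.

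**Illustration of what incomplete reporting does.** With 30 dyads in blocks of 10 and groups of 5, each arm has 30/2 = 15. Assume, purely for illustration, that 10% of adolescents in an arm have a session-related event. The chance that at least one is recorded is 1 − (1 − 0.10 × d)^15, where d is the share that comes to light.

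- d = 1: 1 − 0.90^15 = 0.79
- d = 0.5: 1 − 0.95^15 = 0.54
- d = 0.2: 1 − 0.98^15 = 0.26

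So the chance of an empty count goes from 21% to 46% to 74%. Neither the 10% nor d comes from the documents. The figures show only that silence in an arm of 15 says little unless d is known to be high.

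**The case against.** The strongest reply is that the protocol never says remote sessions are unattended. Interventionists lead both groups, TRUST sessions are audio-recorded, and recordings with exercises could be used inside a phone or video session. This stands. A reader might infer that dyads have no staff contact across the sessions, but the documents do not establish that. They are unclear, and the consequences above are conditional on delivery by recordings alone.

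A reader might also infer that the harms leading to removal could not be observed by anyone. That is too strong: only the disruption ground needs an observed group. Nor is the promised support lost altogether, since the parent, the crisis numbers, the mobile crisis team and the psychologist's review remain. It would likewise be wrong to say that events between surveys are not collected at all, because a reporting route exists. What is missing is any prompt to use it.

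Other data bear on lasting harm. Parent-child coercion, family relationships, closeness, trust, perceived stress and depressive symptoms are measured at baseline, 3 and 6 months, and differential attrition is monitored. These could show persistent conflict by arm. They are not designed to show a short-lived event or to link it to a session activity.

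The audio recordings do not close the gap. They are stated for TRUST only, half are reviewed, and the review checks that topics were covered. Any harm found that way would be found in one arm.

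The remark about parents' reprimands describes the problem that TRUST sets out to address, and dyads are to practise with small truths after discussing it. That is fair context. It also shows that the protocol foresees the reaction, which is the reason to list it as a risk.

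Finally, because both arms use the remote format and randomisation is in blocks, format alone need not bias the comparison between arms. The likelier loss is sensitivity, together with counts that are not comparable between remote and in-person dyads.

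**Conclusion.** The inconsistency between Setting (1) and item h, including its fidelity paragraph, is real and bears on the current mode of delivery. If remote delivery is by recordings alone, one of three removal grounds has no observer, one promised form of support has no remote version, and adverse events between surveys rest on spontaneous report. Under-ascertainment is then likely, to an unknown degree and possibly differing by format. If sessions are live, most of this falls away. What remains is the lack of any scheduled question about events and the disclosure risk missing from the protocol's risk section. The consent pages are not in the text reviewed, so nothing is concluded about them. The point supports a low-cost improvement in safety data; it is not evidence that harm has been missed.

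**What to change.** 1. Reconcile Setting (1) with item h and its fidelity paragraph, stating whether remote sessions are live, recorded or both. State how the study-visit check-in, the research assistant's support and the removal grounds apply remotely.
2. Add the same few fixed items to the 3- and 6-month REDCap surveys in both arms and to the session pre- and post-tests. They would cover upset or conflict after a session activity, feeling unsafe, and wanting a call. The adolescent should answer in private and, where a device is shared, submit before handing it over.
3. Pre- and post-tests are described only for remote delivery, so give any in-person dyads the same session items. Otherwise the fix would itself make ascertainment depend on format.
4. Tabulate the answers by arm and format in the DSMC report.
5. Add conflict after disclosure to Risks to Research Participants.

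How a positive answer is handled is for the investigators to define. The cost is about a minute per form, some protocol wording, and some extra low-grade reports, which should fall equally on both arms.

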Title: Pilot RCT to Evaluate the Effects of a Trust-Building Depression Management Intervention on Moderate Depressive Symptoms in Low-Income Adolescents

NCT: 03599141

Date IRB approved: 10/13/2022

PROTOCOL TITLE: Study comparing two depression management interventions for teens with depression

PRINCIPAL INVESTIGATOR:

[name], RN
Frances Payne Bolton School of Nursing
[contact]
[contact]

UH FACULTY ADVISOR: N/A

OTHER DEPARTMENTS INVOLVED IN THIS STUDY: Department of Psychology

VERSION NUMBER: 1.16

DATE: 09/28/2022

Study Comparing Two Depression Management Interventions for Teens with Depression

Objectives

(1) Our purpose is to test the Trust-building depression Self-Management Together (**TRUST**) intervention among adolescents with moderate depressive symptoms. Our premise is that trust can be learned, that increasing trust will improve self-regulation, and improved self-regulation will influence depression management behaviors, which will decrease depressive symptoms and increase quality of life (QOL). **The study aims are:**

Aim 1. Compare the effects of the TRUST intervention with a depression management intervention on depression management behaviors (sleep, stress management, medication adherence, appointment keeping) and health status (depressive symptoms, QOL) in adolescents with moderate depressive symptoms.

Aim 2. Assess whether the effects of the TRUST intervention on depression management behaviors (sleep, stress management, medication adherence, appointment keeping) and health status (depressive symptoms, QOL) are mediated by (respiratory sinus arrhythmia [RSA], behavioral interaction assessment, adolescent/parent trust self-reports, relationship quality, self-regulation, family cohesion, social support, decision making, self-efficacy, rumination, decentering).

Aim 3. Assess the effects of potential moderators (gender, race, perceived stress, parental monitoring, household income, parent level of education, parenting style, parent stress) on the relationship between the TRUST intervention and depression management behaviors and health status (depressive symptoms, QOL).

(2) **Hypothesis:** We hypothesize that variations in adolescent/ parent trust-building will predict response to the TRUST intervention and depression management behaviors as evidenced by change in depressive symptoms and QOL.

Background

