Inclusion and Exclusion Criteria

(1) **Screening.** Using an existing collaboration with the CMSD school system, participants will be recruited via advertisements in parent meetings at CMSD schools and social media. Candidates whose parents indicate interest by phone call, email, message, or completing an online prescreening tool will be contacted using an IRB approved script to recruit, screen, and enroll participants. Adolescents will complete the PHQ-8 measure of depressive symptoms over the phone or by REDCap link on a tablet computer. A PHQ8 score >8 and <20 will be considered for study inclusion. Screening the adolescent with the PHQ8 confirms that the adolescent currently has moderate depressive symptoms and will occur during the screening process, prior to consent/assent. We have requested a waiver of consent on page 7 for screening purposes.

(2) Inclusion (adolescent)	
1.	A Cleveland Metropolitan School District student
2.	Ages 14-17 years old
3.	Reports diagnosis of depression
4.	Reports moderate depressive symptoms (PHQ-8 score >8 and <20)
5.	Able to read, speak, and understand the English language
Inclusion (parent/guardian)	
1.	Female parent/guardian
2.	Able to read, speak, and understand the English language

(3) Exclusion (adolescent)	
1.	Current suicide risk
2.	Diagnosis with bipolar disorder, schizophrenia, or a personality disorder
3.	Sever behavioral problems that preclude group participation (as reported by parent)
4.	Family plans to move from the region within one year
Exclusion (parent)	
1.	Family plans to move from the region within one year

Number of Research Participants

(1) N = 30 adolescent/parent dyads
 (2) Single site study, N/A

Vulnerable Populations

(1) Vulnerable populations included are:

- Adults unable to consent**
- Minors (infants, children, teenagers)**
 - Wards of the state
 - Foster Children
- Pregnant Women**

- Neonates**
- Employees of CWRU or UHHS**
- Prisoners**
- Illiterate Individuals**
- Non-English Speaking**
- University Students**

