We will not be providing individual results to participants’, however, general group results will be shared with participants at the end of the study, or as needed if the results may influence their decision to remain in the study.

Study Design, Procedures, and Timeline

(1) Study Design. We will use an exploratory 2-group pilot RCT to investigate the hypothesized effects of the TRUST intervention on depressive symptoms, QOL, sleep, stress management, medication adherence, and appointment keeping at 3 months and 6 months in comparison to the effects of a Depression Management Intervention.

(2 & 3) Research Procedures will include:

- a. **Recruitment and Informed Assent/Consent:** We will recruit participants using an IRB-approved protocol. All participants will be required to give informed written assent/consent to participate in the project. During the COVID-19 pandemic, we will be

obtaining assent/consent online via REDCap. Research assistants will read, review, and discuss assent/consent forms with all potential participants prior to asking them to sign. If the candidate appears confused or indicates a lack of understanding, the interviewer will attempt to identify the misunderstanding and to explain the form again. Any candidate who still does not comprehend the form will be excluded from the study. We will ask questions to confirm understanding of the material covered in the assent/consent procedure (e.g., "Could you tell me what's going to happen if you enroll in the study?"). Interviewers will witness and date the signed forms. Assent/consent procedures will take place in a private room or office. PI [name] will keep assent/consent forms in a secured file cabinet within a locked room. Participants will be enrolled in blocks of 10 dyads, using a block randomization scheme to assign each of the 10 dyads to either study group. Once a group of 5 is filled, weekly intervention sessions will begin.

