b. **Questionnaires:** Survey data will be collected using REDCap on a tablet computer. Measures used in the study are listed in the Table below. Due to restrictions associated with the COVID-19 pandemic, parents and adolescents will be asked to answer questions privately and at approximately the same time point on an electronic device connected to the internet in their homes. If, for example, only one electronic device is able to connect to the internet, the adolescent can complete the survey and then pass the device to the parent for survey completion. We are assessing families for internet access and device availability in the screening form. For families that do not have a device, we will mail them a tablet that they will mail back to us at the end of the study.

Study Variables, Measures, and Data Collection Points						
ADOLESCENT SURVEY						
Variable	Instrument	Title on Survey	B	3M	6M	
Depressive symptoms	Patient Health Questionnaire-8 ¹⁹	Depression Questions	X	X	X	
Quality of life	Youth Quality of Life-Short Form ²¹	Quality of Life Questions	X	X	X	
Sleep	PROMIS sleep disturbance-4 ²⁵ Children's Report of Sleep Patterns ²²	Sleep Questions More Sleep Questions	X X	X X	X X	
Stress management	Adolescent Lifestyle Questionnaire—stress management subscale ²³	How do you handle your stress?	X	X	X	
Medication adherence	Extent of Medication Adherence ²⁴	Medication Questions	X	X	X	
Appointment keeping	Hill-Bone Compliance Scale ²⁵	Appointment Questions	X	X	X	
Biologic Trust	Respiratory sinus arrhythmia ¹³	Not applicable—assessment in lab	X	X		
Behavioral Trust	Behavioral interaction assessment ¹⁴	Not applicable—assessment in lab	X	X		
Cognitive Trust	Children's General Trust Scale ²⁶	Children's Trust Questions	X	X	X	
Cognitive Trust	Parent Trust of Child Scale—Adolescent perceived ²⁷	Parental Trust Questions	X	X	X	
Relationship quality	Inclusion of Other in Self ²⁸	How close are you with your parent?	X	X	X	
Self-regulation	Positive and Negative Affect Schedule ²⁹	Emotion Questions	X	X	X	

Family cohesion	Brief Family Relationship Scale ³⁰	Family Relationship Questions	X	X	X
Rumination	Children's Response Style Questionnaire ³²	How do you handle sadness?	X	X	X
Self-efficacy	PROMIS Self-efficacy - Youth ³¹	Getting stuff done questions	X	X	X
Decentering	Experiences Questionnaire ³³	Self-awareness Questions	X	X	X
Demographics	Demographics questionnaire	Who are you?	X		
Perceived stress	Perceived Stress Scale-Peds ³⁴	Stress Questions	X	X	X

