	Group 1	Group 2
Prescreening	5 minutes	5 minutes
Screening	30 minutes	30 minutes
Study Visit 1 (Baseline)	30 minutes	30 minutes
Intervention week 1	45 minutes	1 hours
Intervention week 2	45 minutes	1 hours
Intervention week 3	45 minutes	1 hours
Intervention week 4	45 minutes	1 hours
Intervention week 5	45 minutes	1 hours
Intervention week 6	45 minutes	1 hours
Intervention week 7	45 minutes	1 hours
Intervention week 8	45 minutes	1 hours
Study Visit 2 (3 months)	30 minutes	30 minutes
Study Visit 3 (6 months)	30 minutes	30 minutes
Total	8 hours 5 minutes	10 hours 35 minutes

ClinicalTrials.gov Information

Has this study been registered on ClinicalTrials.gov?

Yes. Provide the following:

- i. The ClinicalTrials.gov identifier: 00220503
- ii. Investigator/sponsor responsible for registering: [name]

No. Explain if there are plans to register or why registration is not required.

List of Data to be Collected

1. Indicate what identifiers you will collect

- Name
- Address
- Dates related to an individual (*birthdate*)
- Telephone number
- Fax number
- Email address

- Social security number
- Medical record number
- Health plan beneficiary number
- Account number
- Certificate/license number
- Any vehicle or other device serial
- Device identifiers or serial numbers
- Web URL
- Internet protocol (IP) address
- Finger or voice prints
- Photographic (video) images
- Other: Any characteristic that would uniquely identify the individual

Data Analysis Plan

(1) Statistical Analyses. Each participant will be assigned a unique identifier for tracking purposes and all raw data will be uploaded to the secure database in REDCap. We will explore all variables using descriptive statistics. To address the Aims 1-2, we will use a linear mixed effects model. To address Aim 3, we will apply usual mediation techniques.

Confidentiality of Specimens and Banking

Salivary specimens and cheek swabs are canceled due to Covid-19. Specimens collected prior to Covid-19 were handled as follows. Salivary specimens and cheek swabs will be collected and banked until full processing can occur. The specimens will be stored in the Frances Payne Bolton School of Nursing biomarker laboratory. Specimen testing is funded with internal monies; therefore, specimens will not be transferred to other researchers at this time.

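### Aim 3 asks whether eight variables moderate the TRUST effect, but the analysis plan assigns it mediation techniques, which do not estimate moderation

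*Combined protocol and SAP*

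**What the plan says.** **Objectives, Aim 2** is mediation. It asks whether the effects of TRUST "are mediated by (respiratory sinus arrhythmia [RSA], behavioral interaction assessment, adolescent/parent trust self-reports", and the list continues with "relationship quality, self-regulation, family cohesion, social support, decision making, self-efficacy, rumination, decentering".

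**Objectives, Aim 3** is moderation: "Assess the effects of potential moderators (gender, race, perceived stress, parental monitoring, household income, parent level of education, parenting style, parent stress"), acting on the relationship between TRUST and the outcomes.

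**Data Analysis Plan, (1) Statistical Analyses**, apart from a sentence on descriptive statistics, consists of "To address the Aims 1-2, we will use a linear mixed effects model. To address Aim 3, we will apply usual mediation techniques". It gives no model terms, no interaction and no indirect effect.

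**Study Design** describes the setting: "We will use an exploratory 2-group pilot RCT to investigate the hypothesized effects of the TRUST intervention". The stated size is "N = 30 adolescent/parent dyads".

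**The concern.** Mediation and moderation are different quantities. Mediation asks whether treatment works by changing an intermediate variable. Moderation asks whether the treatment effect differs between people who differ at the outset. An analyst who follows the plan for Aim 3 would report indirect effects through the moderators and no estimate of effect modification.

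An analyst who noticed the problem would have to pick a moderation method outside the plan. Aim 3 pairs eight moderators with six outcome domains (8 × 6 = 48 pairs, or 8 × 7 = 56 if the two sleep instruments are counted separately). That leaves wide room for choices made after the data are seen.

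**Working it through.** **Step 1. Aims against methods.** The plan gives no figure to reproduce, so the check is a side-by-side reading.

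| Aim | Question in Objectives | Method in Data Analysis Plan | Match |
|---|---|---|---|
| 1 | Group comparison on six outcome domains | Linear mixed effects model | Yes |
| 2 | Mediation, 11 listed mediators | Linear mixed effects model | Possible, but no indirect effect, interval or timing given |
| 3 | Moderation, 8 listed moderators | Mediation techniques | No |

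**Step 2. Is it corrected elsewhere?** No section gives a treatment-by-moderator term or a mediator path. Elsewhere, interaction refers to the parent-adolescent laboratory task. Indirect effects appear only in the title of reference 41, which the body text does not cite.

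**Step 3. What the stated method would return.** Write A for arm, M for the candidate variable and Y for the outcome.

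- Moderation: Y = β0 + β1·A + β2·M + β3·A·M. Aim 3 asks for β3.
- Mediation: M = α0 + a·A, and Y = γ0 + c·A + b·M. The indirect effect is a × b.

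The section on questionnaires says "Measures used in the study are listed in the Table below". In that table, the only possible source for gender, race, household income and parent education is the demographics questionnaires, given at baseline only. Arm cannot alter them, so a = 0 and a × b = 0 × b = 0, whatever the value of β3.

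Perceived stress, parental monitoring, parenting style and parent stress are measured at baseline, 3 months and 6 months. Mediation could be run on these four, but a × b would still not be β3.

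**Step 4. Precision of the right quantity (illustrative).** The documents give no SD, effect size or attrition. Assumptions:

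- residual SD of 1 and no losses;
- one follow-up visit, with baseline outcome as a covariate;
- equal arms of 30 / 2 = 15, inferred from "Participants will be enrolled in blocks of 10 dyads, using a block randomization scheme" and groups of five.

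The model has five coefficients, so there are 30 − 5 = 25 degrees of freedom and t = 2.06. The hand formulas ignore the small cost of the baseline covariate.

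- *Continuous moderator, SD 1 in each arm:* SE ≈ √(1/14 + 1/14) = 0.378; half-width 2.06 × 0.378 = 0.78. Simulation, letting the moderator vary by chance, gives 0.82.
- *Balanced binary moderator:* four cells of 30/4 = 7.5; SE = √(4/7.5) = 0.730; half-width 2.06 × 0.730 = 1.50. Simulation gives 1.51 to 1.54, depending on how balance is set.
- *Unbalanced binary moderator:* the Background puts the school district at 84% ethnic minority. Assuming that split in each arm gives cells of 15 × 0.84 = 12.6 and 15 × 0.16 = 2.4; SE = √(2/12.6 + 2/2.4) = 0.996; half-width 2.06 × 0.996 = 2.05. Simulation gives about 2.15.

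**The case against.** **It is an exploratory pilot.** This stands as a limit on severity. It does not remove the mismatch: an exploratory aim still needs a method that estimates what it asks about.

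**The aim numbers were simply swapped, and any reader can see it.** With one mediation aim and one mediation sentence, this is the simplest explanation. The documents do not prove it. The word mediation may instead have been written for moderation, and that reading would leave Aim 2 with a different plan. Only the sponsor can settle it. Renumbering alone would still leave the moderator term, the indirect effect and the timing unstated.

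**Aim 2 has the wrong method too.** A reader might infer this, but the documents do not support it. Mixed models can form part of a mediation analysis. What Aim 2 lacks is detail.

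**Some mediation models include a treatment-by-mediator term, so moderation could emerge anyway.** The plan names no such term. The effect that mediation analysis sets out to report would still be the indirect one.

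**Thirty dyads cannot detect moderation.** Largely fair, as Step 4 shows. That is a reason to report intervals with caution, not to estimate something else.

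**Conclusion.** Wrong as written for Aim 3; missing detail for Aim 2; no effect on Aim 1. None of the eight moderators has a method that estimates effect modification. For four of them the true value of what the stated method targets is zero by design. This conclusion rests on the text alone and needs no numerical assumption, beyond taking the demographics questionnaires as the source of those four variables.

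The half-widths of about 0.8 SD (continuous) and 1.5 SD (balanced binary) depend on the assumptions in Step 4. They are favourable: imbalance or attrition would widen them.

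A reader might infer that the trial's main comparison is compromised, or that correcting the text would make Aim 3 informative. Neither follows. The group comparison keeps a suitable model, and the correction restores the right quantity without supplying adequate power.

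**What to change.** Replace both method sentences in the Data Analysis Plan. Aims 1 and 2 share one sentence, so it has to be split.

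- **Aim 1:** linear mixed effects model, as now.
- **Aim 2:** mediation analysis reporting an indirect effect with a confidence interval and a stated timing, for example mediator at 3 months and outcome at 6 months, adjusted for baseline. Restrict it to participants whose data may be used under the re-consent rules in Consent Process. For those who completed the study and cannot be reached, these rules allow only the depressive-symptom and COVID-19 anxiety surveys.
- **Aim 3:** linear mixed effects model with a treatment-by-baseline-moderator interaction. Use arm-by-visit-by-moderator if baseline is an outcome row, because there is no treatment effect to modify at that visit. Use arm-by-moderator if baseline is a covariate. Report exploratory estimates with confidence intervals, and say that precision at 30 dyads is low.

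The sponsor should confirm that this allocation of methods is what was intended. The cost is wording only: no new data, visits or participants.
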